
Study Methods of Appraisal
	
Methods:
 
During the study the subjects will be evaluated with:
 
 Mandatory – Peregrine Endoscope (the study device) Mandatory – A Standard 30° 4mm endoscope Optional – A Standard 70° 4mm endoscope Optional – A standard Flexible Endoscope 
Safety assessment
 
Safety assessment will be based upon monitoring the Adverse device events, which will be collected throughout the procedures in which Peregrine was used.
 
Performance assessment
 
 Evaluation of ability of Peregrine and the comparison endoscope (a standard 30° endoscope) to access and visualize sinus anatomy (No. of successes divided by No. of attempts): 
 Anatomic landmarks – Maxillary (ostium, anterior wall, lateral aspect, floor), Frontal (ostium, posterior wall, anterior wall, lateral recess), Sphenoid (ostium, sella, floor, lateral recess). Visualization success rates will be confirmed by direct visualization. Level of prior resection will be recorded – anterior or posterior ethmoidectomy, draf IIa, draf IIb, uncinatectomy, antrostomy, maxillectomy, sphenoidotomy, dilation Image quality – will be assessed through a yes/no statement regarding adequacy of Peregrine image quality for office endoscopy procedures, in comparison to the standard endoscope. Patient pain and tolerability will be assessed through validated VAS for both Peregrine and the comparison endoscope. Impact of Peregrine's extended visualization capability on clinical workflow will be evaluated through a series of questions regarding identification of pathology, evaluation of mucosa, change in medical management, need for additional CT scan, indication for revision surgery, etc. Peregrine ease-of-use will be evaluated through a user questionnaire. Irrigation (through Peregrine working channel) will be documented (performed/not performed), when performed.

Inclusion/Exclusion Criteria
	
Inclusion Criteria:
 
 A male or female patient who has had prior ESS and who is indicated for office endoscopy by the ENT specialist Patient age: adult (>18 years old) A patient who is able to understand the requirements of the study, is willing to comply with its instructions and schedules, and agrees to sign the informed consent 
Exclusion Criteria:

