	
 1. Any medical disorder which in the investigator's judgment contraindicates the patient's participation 2. Pregnancy
Study Duration	
Per Patient: up to 1 month
 
A total of 6 months to recruit and treat up 30 patients.

Sample Size Calculations	
The performance endpoint of the study will be to demonstrate that the Peregrine Endoscope will perform comparable to or better than a Standard 30° 4mm Endoscope, where a difference of 20% or more between visualization success rates will be considered to be statistically significant. Per protocol, a sub-group analysis of each of the different sinus cavities (i.e., Frontal, Maxillary and Sphenoid) will be used for power calculation.
 
In order to maintain minimal Power 80% and Type I ($=\alpha$) error of 5% to detect minimal differences of $\pm 20\%$, a sample size of 7 samples is needed per sinus cavity. This number does not include an estimated 20-30% drop-out rate due to technical reasons unrelated to the device. Therefore, a sample size of 10 samples per each sinus cavity, and a total of 30 samples for all sinuses (total of up to 30 patients), will be recruited to the study.

Statistical Analysis Plan	
Demographic and baseline characteristics will be summarized for all subjects included in the analysis. Continuous variables will be summarized using summary statistics (mean, standard deviation, median, range combined with 95% confidence interval calculations) and categorical variables will be summarized using counts and percentages.
 
In particular, the following tests according to the parameters type are going to be performed:
 
 • Continuous parameters will be presented by the estimated value and calculation of 95% confidence intervals. In addition, the comparison will be by using the relevant Student's t-test. • Categorical parameters will be analyzed by Fisher exact test/ chi-square tests (in case of low observed frequencies). 
Tests will be two-sided in accordance to the hypothesis regarding the tested parameters, with a significance level of 0.05.

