4.2 Performance assessment

- To compare visualization success rates of the paranasal sinus anatomy by Peregrine and by standard endoscopes used in the office setting.
- To assess whether the image quality of Peregrine is adequate for endoscopy procedures in the office.
- To evaluate patient tolerability and pain.
- To evaluate Peregrine utility in clinical decision making.

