4.3 Study End Points

Primary - Safety

All adverse device effects will be captured and summarized as defined in **Section-8**. Adverse device effects (type, frequency, severity) are expected to be similar to those reported in the literature for Nasal Endoscopy (section 8).

For this study, the Safety comparison with the data of Nasal Endoscopy reported in the literature will be descriptive with no statistical endpoints.

Primary – Performance

Evaluation of ability of Peregrine and the comparison endoscope to access and visualize sinus anatomy at the following landmarks:

- Maxillary (ostium, anterior wall, lateral aspect, floor)
- Frontal (ostium, posterior wall, anterior wall, lateral recess)
- Sphenoid (ostium, sella, floor, lateral recess)

Subjects will be evaluated with:

- a. Mandatory – Peregrine Endoscope (the study device)
- b. Mandatory – A Standard 30° 4mm endoscope
- c. Optional – A Standard 70° 4mm endoscope
- d. Optional – A standard Flexible Endoscope

- Visualization success rates, calculated as the No. of successes divided by the No. of attempts, will be confirmed by direct visualization.
- Representative images of the accessed anatomic landmarks will be recorded.
- Level of prior resection will be recorded – anterior or posterior ethmoidectomy, draf IIa, draf IIb, uncinatectomy, antrostomy, maxillectomy, sphenoidotomy, dilation

Secondary - Performance

- Image quality – will be assessed through a yes/no statement regarding adequacy of Peregrine image quality for office endoscopy procedures, in comparison to the comparison device.
- Patient pain and tolerability will be assessed through validated VAS for both Peregrine and the comparison endoscope.
- Impact of Peregrine's extended visualization capability on clinical workflow will be evaluated through a series of questions regarding identification of pathology, evaluation of mucosa, change in medical management, need for additional CT scan, indication for revision surgery, etc.
- Peregrine ease-of-use will be evaluated through a user questionnaire.

Other Measurement – Performance and effectiveness

- Irrigation (through Peregrine working channel) will be documented (performed/not performed), when performed.
- To evaluate nasal cavity inflammation and sinuses inflammation using Lund Mackay CT score and Lund Kennedy Endoscopic scoring, if applicable.

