6 INVESTIGATION PLAN

6.1 Study Design

Type of Study

This is an open, single-center, prospective study in which the investigational device, the Peregrine Drivable ENT Scope, will be tested in a single group of adult patients, male or females.

The rationale behind this study is to show that the ability to visualize intra-sinus anatomic landmarks of the Maxillary, Frontal and Sphenoid sinuses is comparable to or better than the ability to visualize them with a Standard 70° 4mm Endoscope in the office setting; This study will evaluate the safety and performance of the Peregrine endoscope which enables intra-sinus visualization as a first step to assess potential benefits, such as minimizing CT scans and associated radiation exposure, change in medication regimen, referral to revision surgery, saving multiple office visits, and cost.

This study is proposed after completing a series of clinical cases with the Sinusway endoscopy system, (which is similar to the Peregrine Endoscopy system) which demonstrated that the system is safe and performed well to physician's satisfaction (detailed information on the studies is provided in the Investigator's Brochure).

Measures to Minimize Bias

Subjects shall constitute their own control group by comparing the ability to visualize intra-sinus anatomic landmarks and pain and tolerability between Peregrine and a standard endoscope in the same subject. For this reason, no randomization is necessary in this study.

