6.2 Study Procedures

Visits 1: Screening and Enrollment

- Screening will take place at the day of procedure or within 1 day-30 days before the procedure as part of a regular office visit.
- Patients who potentially qualify for the study will be offered an Informed Consent to sign prior to further evaluation. Any patients who do not qualify will be exited from the study as screening failures and will not be included in the safety/effectiveness analyses.
- The following assessments will be performed before the procedure for each patient:
 - Medical history (including concomitant medications deemed relevant by the investigator)
 - Sino-Nasal outcome test (SNOT-22)
 - Vital signs – optional
 - CT scan – optional - as available in the patient file.
 - Nasal Cavity and sinuses inflammation score will be captured using the Lund Mackay CT
 - Compliance with inclusion/exclusion criteria
 - Patients found eligible to participate in the study during visit 1 will be scheduled to undergo nasal endoscopy evaluation with Peregrine.

Visit 2: Procedure

The procedure will be office endoscopy as part of a routine post-operative office visit or due to recurrence of symptoms. Visits 1 and 2 can be combined into a single visit.

- **Before the procedure:**
 - Eligible subject/s will attend the Medical Center at the day of procedure and will be inquired by the PI regarding changes to their health status since the screening visit. If at this point it is

determined that the patient **does not** meet all Inclusion and Exclusion criteria and cannot be treated, the patient will be exited from the study. These patients will be considered screening failures and will not be included in any of the safety or efficacy endpoint analyses.

- **Endoscopy:**

1. Patients will undergo the procedure under local or topical anesthesia, at physician discretion.
2. The Peregrine endoscopy system will be prepared for use per its instructions for use.
3. Obligatory – the surgeon will attempt to visualize the pre-defined sinus anatomy landmarks with a standard 30° 4mm endoscope which will be recorded as success/failure, and an image of the anatomic landmarks visualized will be taken. Patient will be asked to score the endoscope for pain and tolerability.

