4. Obligatory – the surgeon will then attempt to visualize the pre-defined sinus anatomy landmarks with Peregrine endoscope which will be recorded as success/failure, and an image of the anatomic landmarks visualized will be taken. Patient will be asked to score Peregrine for pain and tolerability.
5. Optional – the surgeon will have the option to attempt to visualize the pre-defined sinus anatomy landmarks with a standard 70° 4mm endoscope and/or a flexible endoscope which will be recorded as success/failure, and an image of the anatomic landmarks visualized will be taken. Patient will be asked to score the endoscope for pain and tolerability.
6. Optional - irrigation of the nasal anatomy will be performed and recorded as Done/Not Done and which sinus was irrigated.
7. The physician will answer a set of questions related to endoscope usability and utility in clinical decision making in comparison to the standard endoscope.
8. The procedure will be recorded by site's AIDA system to enable the physician to perform assessments post procedure.

- **After the procedure:**

- The patient will recover from the procedure according to center's common practice. Before the patient is dismissed, recording of AE, if any, will be performed. Patient will exit the study.

Visit 3: Telephone Follow-up visit

- Telephone Follow-up for safety assessment will be conducted by study personnel two weeks \pm 3 days following patient last study visit.
- In the absence of any on-going ADE's, the patient will exit the study and Exit Form will be completed.

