7 STATISTICAL CONSIDERATIONS AND SAMPLE SIZE

Statistical Considerations

Demographic and baseline characteristics will be summarized for all subjects included in the analysis. Continuous variables will be summarized using summary statistics (mean, standard deviation, median, range combined with 95% confidence interval calculations) and categorical variables will be summarized using counts and percentages.

In particular, the following tests according to the parameters type are going to be performed:

- Continuous parameters will be presented by the estimated value and calculation of 95% confidence intervals. In addition, the comparison will be by using the relevant Student's t-test.
- Categorical parameters will be analyzed by Fisher exact test/ chi-square tests (in case of low observed frequencies).

Tests will be two-sided in accordance to the hypothesis regarding the tested parameters, with a significance level of 0.05.

Sample Size

Up to thirty (30) patients are expected to complete the study.

The primary endpoint of the study will be to demonstrate that the Peregrine Endoscope will perform comparable to or better than a Standard 70° 4mm Endoscope, where a difference of 20% or more between visualization success rates will be considered to be statistically significant. Per protocol, a subgroup analysis of each of the different sinus cavities (i.e., Frontal, Maxillary and Sphenoid) will be used for power calculation.

In order to maintain minimal Power 80% and Type I ($=\alpha$) error of 5% to detect minimal differences of $\pm 20\%$, a sample size of 7 samples is needed per sinus cavity. This number does not include an estimated 20-30% drop-out rate due to technical reasons unrelated to the device. Therefore, a sample size of 10 samples per each sinus cavity, and a total of 30 samples for all sinuses (total of up to 30 patients), will be recruited to the study.

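### The primary comparator is the mandatory 30° endoscope in the synopsis but the optional 70° endoscope in Section 7

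*Combined protocol and SAP*

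**What the plan says.** The synopsis names the 30° endoscope twice. Its sample-size entry says the study will show that "the Peregrine Endoscope will perform comparable to or better than a Standard 30° 4mm Endoscope". Its performance-assessment entry describes the endpoint as "Evaluation of ability of Peregrine and the comparison endoscope (a standard 30° endoscope) to access and visualize sinus anatomy".

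The body names the 70° endoscope twice. Section 7 calls it the primary endpoint to show that "the Peregrine Endoscope will perform comparable to or better than a Standard 70° 4mm Endoscope". Section 6.1, in the study rationale, wants the ability to see the intra-sinus landmarks to be "comparable to or better than the ability to visualize them with a Standard 70° 4mm Endoscope in the office setting".

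Two other body sections do not say which endoscope is meant. Section 4.3 defines the primary performance endpoint as "Evaluation of ability of Peregrine and the comparison endoscope to access and visualize sinus anatomy at the following landmarks", without the synopsis's parenthesis. Section 4.2 uses the plural: "To compare visualization success rates of the paranasal sinus anatomy by Peregrine and by standard endoscopes used in the office setting".

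The procedures treat the two endoscopes differently. In Section 6.2, step 3 is obligatory: "the surgeon will attempt to visualize the pre-defined sinus anatomy landmarks with a standard 30° 4mm endoscope which will be recorded as success/failure". Step 4, also obligatory, is the Peregrine examination. Step 5 is optional: "the surgeon will have the option to attempt to visualize the pre-defined sinus anatomy landmarks with a standard 70° 4mm endoscope", and/or with a flexible endoscope. The device lists in the synopsis and Section 4.3 likewise mark the 30° endoscope mandatory and the 70° endoscope optional.

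**The concern.** A confirmatory comparison has to name one control before the data are seen. Here the same claim is attached to two controls, and the one named in the body's statistical section need not be used in any patient.

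Three things are at stake.

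- Section 7 cannot be carried out as written if few or no 70° examinations are done.
- Any 70° data would come from a subset chosen by the surgeon. The study is open and step 5 is listed after the 30° and Peregrine steps, so the choice may follow knowledge of those results. A subset picked that way does not give an unbiased comparison of success rates.
- The text supports either comparator, so the primary one could be settled after the results are known. Nothing suggests that this is intended, but nothing rules it out.

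Section 4.3 uses the same unspecified term for the control in the pain and tolerability scores, so the ambiguity also reaches a secondary endpoint.

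**Working it through.** **Passages side by side**

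| Place | Comparator |
|---|---|
| Synopsis, performance assessment | 30° |
| Synopsis, sample size | 30° |
| Section 4.2 | not specified, plural |
| Section 4.3, primary performance endpoint | not specified, singular |
| Section 6.1, rationale | 70° |
| Section 6.2, step 3 (obligatory) | 30° examination performed |
| Section 6.2, step 5 (optional) | 70° examination at the surgeon's choice |
| Table 1 | not specified, singular |
| Section 7, sample size | 70° |

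The synopsis and Section 7 sample-size texts are otherwise nearly identical, including every number. Each is a complete sentence in current text, so the difference is not a redaction, an extraction fault or superseded wording.

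**Inputs for the size of the problem (Section 7, repeated in the synopsis)**

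- Evaluable samples needed per cavity: 7.
- Planned samples per cavity: 10. The synopsis's study-procedures entry gives 10 as a minimum.
- Drop-out *d*: 20% to 30%.

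**The plan's own figures**

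The step from 7 to 10 reproduces: 7/(1 − 0.20) = 8.75, rounded up to 9, and 7/(1 − 0.30) = 10. The 7 itself can be neither confirmed nor refuted, because no success rate is given for any endoscope. That is a separate question, and this point does not depend on it.

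**70° examinations needed**

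If *d* applies to 70° examinations (assumption), 7 evaluable samples need 7/(1 − *d*) examinations, which is 9 at 20% and 10 at 30%. This count does not depend on how many samples are recruited. With 10 samples, the option must be used in 9 or all 10.

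**Expected 70° samples out of 10 at use rate *u* (assumed; the plan gives none)**

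Expected evaluable samples = 10 × *u* × (1 − *d*).

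| *u* | 70° examinations, no drop-out | Evaluable, *d* = 20% | Evaluable, *d* = 30% |
|---|---|---|---|
| 0% | 0 | 0 | 0 |
| 25% | 2.5 | 2 | 1.75 |
| 50% | 5 | 4 | 3.5 |
| 75% | 7.5 | 6 | 5.25 |
| 100% | 10 | 8 | 7 |

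The break-even use rate is 7/(10 × (1 − *d*)): 70% with no drop-out, 87.5% at 20% and 100% at 30%.

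**The 30° examination under the same drop-out**

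10 × (1 − *d*) = 8 at 20% and 7 at 30%, so the obligatory examination is expected to yield the plan's 7.

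**The case against.** The best reply is that this is a drafting slip with an obvious answer. Besides Peregrine, the 30° endoscope is the only mandatory device in Section 4.3 and the only obligatory one in Section 6.2. Several passages speak of a single standard endoscope, and just two sentences say 70°. One of those, in Section 6.1, is rationale and not a formal hypothesis, so the formal conflict lies between the synopsis and Section 7. The synopsis also has its own sample-size and analysis entries, which name 30° or are compatible with it. On either reading the 30° data are collected.

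Much of this stands: 30° is the more likely intention. It does not settle the matter, because 70° appears in two differently worded sentences in separate sections, one of them the statement of the primary endpoint, and no passage expressly overrides them.

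The use rates are assumptions, and so is the application of drop-out to 70° examinations. If drop-out instead removes whole samples, 8 of 10 remain at 20%, and a 70° examination in 7 of those 8 would be enough. At 30%, all 7 remaining samples would need one. The guaranteed minimum of 0 needs none of these assumptions.

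It is also fair to say that reaching 7 samples with the 30° endoscope does not show that comparison to be adequately powered, since the 7 cannot be verified.

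**Conclusion.** The inconsistency is real and must be resolved before analysis. The primary comparator differs between the synopsis (30°) and Section 7 (70°, supported by Section 6.1), and only the 30° comparison has required data. As written, Section 7 is guaranteed 0 comparator samples per cavity against a stated need of 7. That figure follows from the text alone.

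Under the plan's drop-out and assumed use rates, the optional 70° examination would reach an expected 7 only if used in nearly every sample. At 50% use it gives 3.5 to 4. The conclusion does not depend on whether 7 is the right sample size.

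**What to change.** Ask the sponsor to confirm the primary comparator. Given the synopsis and obligatory step 3, 30° is the choice the data collection already supports. Then, before any analysis:

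- in the comparison statements of Sections 6.1 and 7, replace 70° with 30°;
- in Section 4.3, add the synopsis's parenthesis identifying the comparison endoscope as the 30° one, and use the same singular term in Section 4.2;
- add one sentence making 70° and flexible-endoscope comparisons secondary and descriptive, reported in the subset examined, with its size.

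The cost is a few wording changes in four sections. No examination or data item is added, and no stated number changes, although this edit does not in itself justify the 7. The sponsor gives up a formal claim against the 70° endoscope, which optional, surgeon-selected data could not reliably support. If the sponsor did intend 70°, the present data-collection plan does not guarantee the data for that comparison, and the passages would have to be reconciled on that basis.

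### The plan aims to show Peregrine comparable to or better than a standard scope, but no result is defined that would show it comparable; the only tests named look for a difference.

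*Combined protocol and SAP*

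**What the plan says.** **Aim.** Section 7 (Sample Size) says the primary endpoint is to demonstrate that Peregrine "will perform comparable to or better than a Standard 70° 4mm Endoscope". The synopsis has the same aim with a different comparator: "will perform comparable to or better than a Standard 30° 4mm Endoscope". Section 6.1 gives the aim as the study rationale, again naming the 70° scope.

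**Criterion.** The only number attached to the aim is in the same sentence: "where a difference of 20% or more between visualization success rates will be considered to be statistically significant". The next paragraph of section 7 uses the same 20% as the difference to be detected with 80% power and 5% type I error, and concludes that "a sample size of 7 samples is needed per sinus cavity", raised to 10 for drop-out.

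**Tests.** Section 7 states "Categorical parameters will be analyzed by Fisher exact test/ chi-square tests (in case of low observed frequencies"), and "Tests will be two-sided in accordance to the hypothesis regarding the tested parameters, with a significance level of 0.05". The hypothesis mentioned there is not written down anywhere. Confidence intervals are assigned to continuous variables; categorical variables get counts and percentages.

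**Endpoint.** Section 4.3 lists four landmarks for each sinus type and says "Visualization success rates, calculated as the No. of successes divided by the No. of attempts, will be confirmed by direct visualization". Section 6.1 makes each subject his or her own control, so the data are paired.

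**Descriptive status.** Section 4.3 makes only the safety comparison descriptive: "For this study, the Safety comparison with the data of Nasal Endoscopy reported in the literature will be descriptive with no statistical endpoints". Nothing similar is said of performance.

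**The concern.** A difference test can support *better*: p < 0.05 in Peregrine's favour. It cannot support *comparable*, because failing to find a difference is also what a small study of a worse device produces, and fewer data make that outcome more likely. To show comparability, a plan must say how much worse the device may be and require the data to exclude anything beyond that. This plan does neither, although comparability is half of its primary performance aim. Nothing in it would stop a non-significant result from being reported as the aim achieved.

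**Working it through.** **Inputs from the documents.** 7 samples per cavity, 10 after drop-out, 30 in total; four landmarks per sinus (10 × 4 = 40 per cavity); two-sided 0.05 Fisher/chi-square; a 20-point difference. **Assumed,** because the documents give no success rates: comparator success of 80, 85, 90, 95 and 100%; discordance between scopes of 5–30%.

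**1. The plan's own figure.** The drop-out step reproduces: 7/(1 − 0.3) = 10. The 7 does not, as a test for a 20-point difference. For two proportions, n = [z₀.₉₇₅√(2p̄q̄) + z₀.₈√(p₁q₁ + p₂q₂)]²/d². At the favourable pair 100% and 80% this is [1.96 × √0.18 + 0.842 × √0.16]²/0.04 = 34.1, so 35 per scope (27 one-sided). Values near 7 appear only under assumptions the plan does not state, such as non-inferiority with both rates near 98%. So the sample size does not reveal an intended comparability rule.

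**2. Routes to *comparable*.** The synopsis and sections 4.3, 6.1 and 7 contain no non-inferiority or equivalence hypothesis, no margin with a direction, and no confidence-limit rule. Only the difference tests and the 20% sentence remain.

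**3. Does the 20% sentence agree with the named test?** Fisher p-values with 10 samples per scope:

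| Observed | Gap (points) | Fisher p |
|---|---|---|
| 10/10 vs 8/10 | 20 | 0.47 |
| 10/10 vs 6/10 | 40 | 0.087 |
| 10/10 vs 5/10 | 50 | 0.033 |

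At n = 10 no gap below 50 points reaches p < 0.05 (40 points by uncorrected chi-square). At n = 7 it takes 5 of 7, or 71 points.

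**4. Chance of non-significance when Peregrine is truly worse.** For comparator success p and deficit d, sum Bin(a; n, p) × Bin(b; n, p − d) over all (a, b) with Fisher p ≥ 0.05. Outcomes are taken as independent; ranges run over the five assumed comparator rates.

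| Unit and level | 20 points worse | 30 points worse | 40 points worse |
|---|---|---|---|
| 10 sinuses, one cavity | 94–97% | 84–87% | 63–75% |
| 30 sinuses pooled | 43–70% | 8–40% | 1–15% |
| 40 landmarks, one cavity, treated as independent | 16–59% | 1–25% | 0–5% |

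A paired test alone does not help at n = 10. Exact McNemar needs 6 losses and no win (2 × 0.5⁶ = 0.031; five give 0.0625). If discordance is losses only, it is non-significant 99%, 95% and 83% of the time at 20, 30 and 40 points worse.

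**5. What a proper rule would deliver.** Take M = 20 points, equal devices, and a paired score interval whose lower limit must exceed −M. With no discordant pair among 10, the limit is −z²/(n + z²) = −3.84/13.84 = −27.8%, which fails. Passing needs at least 2 Peregrine-only successes with no loss, or 4 with one loss. Summing the multinomial probabilities with wins and losses equally likely:

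| Independent pairs | 5% discordance | 10% | 20% | 30% |
|---|---|---|---|---|
| 10 (one cavity) | 2% | 6% | 11% | 13% |
| 21 (30 less 30% drop-out) | 72% | 60% | 45% | 35% |
| 30 (pooled) | 90% | 78% | 61% | 50% |

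**The case against.** **The unit may be the landmark, or the comparison pooled.** Success is scored on landmarks, no sinus-level success is defined, and section 7 calls the per-cavity analysis a subgroup analysis used for the power calculation. A reader might infer from the per-cavity figures that a clearly worse device would usually escape detection. The documents do not support that in general. It holds with the sinus as unit and 10 per cavity. With 30 pooled sinuses, 30- and 40-point deficits are usually detected, and with 40 independent landmarks nearly always at 40 points. Landmarks within a patient are unlikely to be independent, so that last row is optimistic. This objection stands as to size; it does not supply the missing criterion.

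**The 20% may be meant as a margin, or as a literal cut-off.** The text calls it neither a margin nor a tolerable loss, gives it no direction, and next uses it as a difference to detect. The likeliest reading is a badly worded design difference. A reader might instead infer a decision rule on observed rates, which with equal devices and n = 10 would fire 11% of the time at 95% success and 49% at 60%. The wording does not exclude this, but it is the less natural reading. The clash with Fisher also depends on the unit: 36/40 against 28/40, also 20 points, gives p = 0.048.

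**The misuse is inferred.** The plan never says that non-significance will be called comparable. That is so, but it offers no other route.

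**This is a small first-step study.** Then a descriptive comparison is the natural choice. As written, the plan claims a demonstration with 80% power and 5% error.

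**Power under a new rule depends on the interval method.** A normal approximation gives 81%, 52% and 29% for 10 pairs at 5, 10 and 20% discordance, far above the score-interval figures. It is unreliable here, since zero discordance in 10 pairs still leaves −27.8%. The missing rule is the same either way.

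**Conclusion.** The concern holds. The primary performance aim has no success criterion for *comparable*, and the analysis named can reach that word only through non-significance, which cannot establish it. The 20% sentence does not fill the gap: it is not a margin, and it contradicts the named tests at the planned 10 samples. This follows from the text without any assumed rates.

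The size is conditional. For a true 20-point deficit, Fisher is non-significant from 94–97% of the time (10 sinuses per cavity) down to 16–59% (40 independent landmarks). These ranges rest on assumed comparator success of 80–100% and independent outcomes. The point should be corrected before analysis because it concerns the primary conclusion and the remedy is wording.

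**What to change.** In the synopsis and section 7, delete the clause that makes a difference of 20% or more statistically significant. Then choose one of two courses.

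**(a) Descriptive.** State that the performance comparison is descriptive, as section 4.3 already does for safety. Report the paired difference in success rates with a 95% confidence interval per cavity and overall, and withdraw the 80% power claim.

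**(b) Keep the claim.** Name the single comparison it applies to (for example all sinuses pooled) and its unit. Suggested text: *The difference in visualization success, Peregrine minus the comparator, will be estimated with a two-sided 95% confidence interval for paired data that allows for clustering within patient. Comparable is concluded only if the lower limit is above −M, and better only if it is above 0. Per-cavity results are reported as estimates with confidence intervals.* The sponsor must state and justify M beforehand (20 points could serve if justified) and restate the power for this rule.

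**In either case,** reconcile the comparator: 30° in the synopsis and as the obligatory scope in section 6.2; 70° in sections 6.1 and 7, although section 6.2 makes the 70° scope optional.

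**Cost.** Course (a) needs wording only. Course (b) needs no extra patients to adopt, but *comparable* becomes harder to declare and the stated 80% power no longer stands. At M = 20 points and 5–30% discordance, equal devices pass 2–13% of the time per cavity with 10 sinus pairs, and 50–90% with 30 independent pooled pairs. A well-powered claim may need more pairs.
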